## **Data Collection**

Participants will be asked to complete baseline measures on Qualtrics before they are randomized to the intervention or control group, which will include demographics (e.g., age, gender, academic year in university), affective attitudes towards exercising, social support,

flourishing, exercise-related subjective vitality, exercise identity, and exercise behaviour. Participants will be provided 10 dollars for completing the baseline questionnaire. Each week, participants will be sent an email to record their exercise in the following week. They will be asked to log the type of exercise and the duration of the activity. At the end of the study (Week 8), participants will be asked to complete an online post-intervention assessment, via Qualtrics, of satisfaction with the program (intervention group only), affective attitudes towards exercising, social support, flourishing, exercise-related subjective vitality, exercise identity, social identification with the running group (intervention group only), and exercise behaviour. Participants will also be provided 10 dollars for completing the post-intervention questionnaire. Finally, 10 participants in the intervention group will be chosen at random to complete semi-structured interviews assessing the feasibility and acceptability of the intervention. Participants will be offered 20 dollars for completing the interview.

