Official Title: The UBC Socializing Together While Running InDEpendently (STRIDE) Pilot  
Trial: A Social Identity Informed Virtual Running Group Program

Protocol ID: H20-03151

NCT ID: Not yet assigned

Last Protocol Update To the University of British Columbia Behavioural Research Ethics Board:  
March 31st, 2021

Protocol Re-Submission Date to clinicaltrials.gov: February 24, 2022

**Rationale:** The current COVID-19 context has resulted in a decrease of physical activity behaviour among Canadian adults (Rhodes et al., 2020). The transition to post secondary education is also associated with decreases in physical activity (Winpenny et al., 2020). With that said, there is a need to support university students' physical activity behaviour, and provide safe opportunities for social interaction, as these are viable coping strategies during the current COVID-19 pandemic (Faulkner et al., 2020). In the proposed randomized controlled pilot trial, the purpose is to examine the feasibility and acceptability of social identity informed virtual running groups to support University of British Columbia (UBC) undergraduate students' well-being. Secondary outcomes include changes in UBC students' exercise identity, perceived social support, exercise behaviour, and well-being. Should the results suggest the intervention is feasible and acceptable, it can inform the development of a larger scale efficacy trial. The pilot intervention can also inform ideal ways to support university students' exercise behaviour and well-being during the pandemic.

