**Aims:** Given the proposed study is a pilot trial, the main purpose is to assess whether the intervention is feasible, and determine participants' acceptance of the program. Various markers of program feasibility and acceptability will be assessed, such as (a) university students' interest in the program, and feasibility of recruitment, (b) participant satisfaction with virtual running groups, (c) affective attitudes towards exercising, (d) participant adherence to the program and control condition, (e) participation rates of group activities, (f) completion rates of assessments, and (g) participants' perception of whether a virtual running group provided adequate social connection.

Although formal hypothesis testing of efficacy is ill-advised in pilot studies given their lack of power (Eldridge et al., 2016), we will examine secondary outcomes that have theoretical and practical importance for exploratory purposes, and calculate statistical information such as effect sizes and measurement variance for informing power analyses when planning future efficacy trials. The secondary outcomes include changes in perception of social support in the context of exercise, global well-being (i.e., flourishing), exercise related well-being (i.e., subjective vitality), exercise identity, and exercise behaviour. Participants' ratings of social identification with their running group will also be assessed at the end of the program (Week 8).

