**Research Design:** The study will utilize a two-arm, parallel group, unblinded randomized controlled pilot trial design. UBC undergraduate students ( $N = 60$ ) will be equally randomized to either an eight-week social identity building virtual running group ( $n = 30$ ) or an eight-week control group ( $n = 30$ ). The group component of the intervention will be delivered via Zoom to support social connection among running group members and the fitness/social media app Strava so participants can post their runs and walks for members of their running group to view and provide words of encouragement. The virtual component is utilized to adhere to physical distancing protocols associated with the current COVID-19 pandemic. The attention control group will receive information regarding physical activity guidelines, be encouraged to meet the Canadian physical activity guidelines, and be asked to record their runs and walks on Strava. The use of an attention control condition will enable us to control for any potential effect of tracking exercise on outcomes such as well-being, exercise identity, and exercise behaviour.

**Study Population:** The target population are UBC undergraduate students (18+ years and enrolled in part time or full time studies) that have been underactive (i.e., not meeting the Canadian guidelines of 150 minutes of moderate-to-vigorous exercise per week) in the past month. Participants must be able to speak and read English, be living in Canada, and not experience any health contraindication that might prevent that person from participating in moderate-to-vigorous intensity exercise. Participants must own a smartphone so they can record their runs and walks on Strava, and have access to the internet and own a device that has camera functionality (e.g., computer) for attending the virtual coffee chats hosted on Zoom.

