group they are in by phone and email. Participants in the intervention condition will be directed to the UBC Canvas portfolio and asked to attend the first meet-and-greet meeting facilitated by the student investigator. During the meet-and-greet, participants will be (a) introduced to the Canvas materials that facilitate their participation in the running group, (b) provided instruction for Strava use, (c) provided information about the group goal, (d) provided explanation of the weekly structure of the program, (e) provided running and exercise considerations (hydration, nutrition, warm-up, safety, footwear and clothing, running pacing), as well as instructed to inform their physician if they experience negative symptoms when exercising (e.g., difficulty breathing) (f) asked to introduce themselves to their running group and brainstorm a team name. The Canvas website will include (a) information about the study (e.g., group goal explanation, Strava instructions), (b) a weekly video providing tips on running (from YouTube), (c) a videoconferencing link for the weekly coffee chats, and (d) discussion questions for the weekly coffee chat. The student investigator will coordinate the completion of the baseline and post-intervention surveys, as well as weekly exercise logs.

We will use a rolling recruitment strategy. As soon as the first 12 participants are recruited, they will be randomized to the virtual running group program or the control group, and begin participation (i.e., cohort 1). If more than 12 participants are recruited (e.g., 24 participants), then 2 cohorts will be created and will begin participating at the same time. Therefore, multiple cohorts will likely begin participation in the study at different time points. We will aim for five cohorts in total (N = 60).

**Randomization:** Once participants complete the baseline questionnaire, they will be randomized to the intervention group (n = 30) or the control group (n = 30) using a random number generator. We aim for 50% recruitment of men and 50% recruitment of women. We will stratify to ensure equal distribution of men and women across conditions. Sequence generation will be completed separately for men and women using the randomizer.org tool for researchers, with blocks of 2 unique numbers (1, 2) with each number designating one of the two randomization groups. Participants will be randomized in the order they complete the baseline survey.

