**Assessment and remuneration:** Participants in both conditions will be provided with \$10 for completing the baseline survey, and \$10 for completing a post-intervention survey. Participants who complete 100% of the weekly exercise logs will receive \$15, and participants who complete at least 75% (i.e., 6-7 logs) of the logs will receive 10\$. Participants in the virtual running group program (n = 10) will be asked to complete a post-intervention semi-structured interview, with the student investigator, assessing their experiences with the STRIDE program. If more than 10 participants indicate interest in participating in the interview, we will select those to be interviewed by a random draw. Interviews will be conducted via Zoom (although only the audio component of the conversation will be recorded). Participants who complete the interview will be provided \$20 for their time.

**Virtual Running Group Condition:** Participants in the virtual running group will be placed into running groups of six people. Each running group will be given the group goal/challenge to collectively run/brisk walk the distance across the province of British Columbia (i.e., from UBC to BC/Alberta Border), for a total distance of 940 kilometers. Individuals have the choice to determine how they will contribute to the collective goal. On average, if each individual were to

complete 20 km a week ((20 kilometers \*6 individual)\*(8 weeks)), that would equal 960 kilometers traveled for the total group across eight weeks. The group running program refers to the shared activity approach in social identity building interventions (Steffens et al., 2019), whereby each individual in the group simultaneously runs/walks, and interdependently work together to achieve the collective goal of running 940 km. The collective goal will be implemented with the purpose of providing members with a shared sense of 'we' and 'us', a common purpose and meaning behind group activity, and will help establish the running group as a distinct group (Levy et al., 2018).

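### Neither arm's listed measures collect injuries, symptoms or reasons for stopping, so the pilot cannot report harms or say how many stops were injury-related

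*Combined protocol and SAP*

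**What the plan says.** Study Population admits underactive undergraduates who do "not experience any health contraindication that might prevent that person from participating in moderate-to-vigorous intensity exercise". Virtual Running Group Condition and Control Condition both set an aim of 150 minutes of moderate-to-vigorous exercise a week.

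Data Collection describes the weekly log: "They will be asked to log the type of exercise and the duration of the activity". The same section lists the Week 8 survey: satisfaction and social identification (intervention arm only), affective attitudes, social support, flourishing, vitality, exercise identity and exercise behaviour.

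Aims names "participant adherence to the program and control condition" among the feasibility markers. Retention defines four percentages: adherence to the program, logs completed, Zoom meetings attended and post-intervention questionnaires completed. Analysis Plan gives frequencies for these.

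The one statement about symptoms during the trial is in Recruitment, within the meet-and-greet content for the intervention arm. Participants there are "instructed to inform their physician if they experience negative symptoms when exercising".

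On the purpose of the pilot, Rationale says: "Should the results suggest the intervention is feasible and acceptable, it can inform the development of a larger scale efficacy trial".

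**The concern.** The trial asks people who have been underactive to take on a substantial weekly amount of exercise, and its main question is whether the program is feasible and acceptable. For such a program, whether participants were hurt or unwell, and why some stopped, is part of the answer. If the plan is followed as written, neither is collected systematically, and neither can be reliably recovered afterwards.

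Two things are at stake. First, the larger trial would be designed without a harms summary from either arm. Second, a low adherence or retention percentage would come without its causes. Someone who stops because of a knee injury and someone who stops for lack of time count the same.

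Log completion does not help. Assessment and remuneration pays for returned logs ("Participants who complete 100% of the weekly exercise logs will receive" the higher payment), and an injured participant can return a log showing little or no exercise. A high completion percentage is therefore compatible with any number of injuries.

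There is also a plain safety asymmetry. Controls have a similar exercise aim, but no symptom advice is described for them.

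**Working it through.** The documents state no harms figure to reproduce, so the check is mainly a comparison of the listed sources.

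**Step 1. What each source can yield**

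| Source (section) | Arm | Content | Injury or symptom count? | Reason for stopping? |
|---|---|---|---|---|
| Eligibility (Study Population) | Both | Contraindication criterion at entry | No, entry only | No |
| Meet-and-greet (Recruitment) | Intervention | Warm-up, footwear, pacing, safety; symptoms go to own physician | No, not routed to the study | No |
| Weekly log (Data Collection) | Both | Type and duration | No | No |
| Week 8 survey (Data Collection) | Both | Psychosocial scales, exercise behaviour; satisfaction and social identification in intervention arm only | No | No |
| Coffee chats (Virtual Running Group Condition) | Intervention | Group talk on progress and challenges; no stated data capture | No | No |
| Interviews (Participant Interviews) | 10 intervention participants | Experiences, strengths, limitations | Not a count; may surface informally | May surface informally |
| Retention; Analysis Plan | Both, as applicable | Percentages and frequencies | No | No |

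No row gives a count in either arm. For controls, no row offers even an informal route.

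**Step 2. How far the interviews could stand in**

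Suppose *k* of the 30 intervention participants stopped because of injury (*k* is assumed), and 10 of the 30 are interviewed purely at random. The chance that none of the *k* is interviewed is C(30−*k*, 10) / C(30, 10).

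- *k* = 1: 20/30 = 67%
- *k* = 2: (20 × 19)/(30 × 29) = 380/870 = 44%
- *k* = 3: (20 × 19 × 18)/(30 × 29 × 28) = 6,840/24,360 = 28%

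Under Assessment and remuneration, a random draw is made among those who express interest if more than ten do. People who stopped early may therefore be less likely to be reached than these figures imply. No control is interviewed.

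**Step 3. What collection would give at this sample size**

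If the item were added and nobody reported an event, the exact two-sided 95% upper limit would be 1 − 0.025^(1/*n*).

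- One arm, *n* = 30: 11.6%
- Both arms, *n* = 60: 6.0%

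Zero is only a reference case, since an item on any limiting injury or symptom will probably draw some positive answers. The limits are wide, so the result would be descriptive.

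**Step 4. Exposure**

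The plan's own example reproduces: 20 km × 6 people × 8 weeks = 960 km. The 940 km goal itself gives 940 / (6 × 8) = 19.6 km per person per week. This is a group average. The plan says "Individuals have the choice to determine how they will contribute to the collective goal", and brisk walking and converted leisure exercise count.

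**The case against.** The best case against the point is that this is a small, low-risk pilot of self-paced exercise that already takes sensible precautions. People with contraindications are excluded, the meet-and-greet covers safety and pacing, and chats and interviews let problems surface. The percentages in Retention and Analysis Plan are computable exactly as defined, no planned estimate is biased, and no progression threshold is stated that a breakdown by cause would alter. All of that stands, and it limits how serious the point is. It does not fill the gap: the precautions are not data, and those described at the meet-and-greet, chats and interviews reach only the intervention arm.

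A reader might infer more than the documents support:

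- **That the trial has no incident reporting at all.** The consent text is not in the material, the information letter is a separate document, and the questionnaires and interview guide are summarised, not reproduced. The supportable claim concerns the listed measures and analyses.
- **That the adherence or retention figures are wrong.** They are not. They lack causes.
- **That a breakdown would separate a fault in the exercise targets from a fault in the group content.** Controls have no group content and both arms share the 150-minute aim, so the split would not isolate the group program.
- **That each participant must run about 20 km a week.** That figure is an average across self-chosen contributions.
- **That weekly symptom screening with formal escalation is needed.** That is more than this gap calls for.

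**Conclusion.** The point holds for the listed measures and analyses. They provide no systematic collection of injuries, symptoms or reasons for stopping in either arm, and symptom advice is described for the intervention arm only. The consequence is an omission from the feasibility answer, not an error in a planned calculation.

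In extent, it affects all 60 participants. The 30 controls have no described route, formal or informal, by which an injury would become known to the study. The ten interviews could miss every injury-related stop with a chance of 67%, 44% or 28% for one, two or three such people, assuming a purely random draw from all 30. How many injuries or stops to expect cannot be stated, because the documents give no rate.

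The conclusion assumes that the summaries of the log and surveys are complete. Incident-reporting wording in the consent text would soften the safety side. By itself it would not put a harms summary or reasons for stopping into the Analysis Plan. The change is worth making because it is cheap and the information is hard to recover later. It is not a reason to hold up the trial.

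**What to change.** 1. Add one yes/no item in both arms asking whether an injury or symptom stopped or limited exercise. Follow a yes with a brief description and whether medical care was sought, so that minor soreness is separated from more serious events. The weekly log is the better place; the Week 8 survey is the minimum.
2. When a participant withdraws or stops returning logs, record the main reason. Report those who do not answer as unknown.
3. In the Analysis Plan, report counts and percentages by arm, descriptively, beside adherence and retention. Do no between-arm test.
4. Give controls the same written advice to contact a physician about negative symptoms.

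The cost is an ethics amendment, a slightly longer form, and the existing team having to read the answers. That team already has the contact: "The student investigator will coordinate the completion of the baseline and post-intervention surveys, as well as weekly exercise logs". On the weekly log this means at most 60 × 8 = 480 responses: 12 a week for one cohort, and 5 × 12 = 60 a week if all five cohorts overlap. The Week 8 minimum means at most 60 responses. No visits or survey rounds are added. Reasons will stay unknown for people who never reply.

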## **Primary Feasibility and Acceptability Outcomes**

### **Interest in Program**

University students' interest in the program will be assessed by recording the number of individuals expressing interest in the program.

### **Participant Enrolment**

Participant enrolment will be assessed with the total number of participants enrolled in the study.

### **Affective Attitudes towards Exercise**

Participant's affective attitudes towards exercise will be assessed using four bipolar semantic differential adjectives (Conner et al., 2011) on a seven-point scale (pleasant-unpleasant; enjoyable-unenjoyable; exciting-boring; satisfying-unsatisfying). Items will be prefaced with: "For me, to participate in regular exercise is..." (Hoyt et al., 2009).

### **Satisfaction with the Program**

One item, adapted from a pilot study conducted by Vincze et al. (2018), will be used to assess general satisfaction with the program: "How satisfied are you with the STRIDE program?". The item will be prefixed with: "Please indicate your agreement with the following statement." Participants will respond to the item along a five-point agreement scale.

### **Retention**

Participant retention will be measured by recording the percentage of individuals who adhered to the program, percentage of weekly exercise logs completed, percentage of weekly Zoom meetings attended, and percentage of post-intervention questionnaires completed.

### **Participant Interviews**

Ten individuals within the intervention group will be recruited to participate in semi-structured interviews via Zoom to discuss the feasibility and acceptability of the intervention. Participants will be asked about their experiences with the program, and their perceived strengths and limitations with the program. Participants will also be asked if they felt the program provided opportunities for social connection, supported their exercise behaviour, and whether they would recommend a similar program to a friend.

## **Secondary Outcome Measures**

### **Perceived Social Support Received in the Context of Exercise**

Social support in the context of exercise will be assessed using four items from past social identity research (Gleibs et al., 2011; Haslam et al., 2005). The items will be prefaced with: “Please rate your agreement with each of the following statements as they relate to the support you receive for physical activity participation.” Participants will respond to the items on a five-point Likert-type scale.

### **Global Well-Being**

Participants will complete the eight-item Flourishing Scale (Diener et al., 2010)

### **Exercise Related Well-Being**

Participants will complete the six-item (Bostic et al., 2000) Subjective Vitality Scale (Ryan & Frederick, 1997) adapted for the context of exercise behaviour.

### **Exercise Identity**

Participants will complete the nine-item Exercise Identity Scale (Anderson & Cychosz, 1994).

### **Social Identity**

Participants in the intervention condition will complete four adapted items (Doosje et al., 1995) assessing their social identification with the running group (control participants will not receive these questions).

### **Exercise Behaviour**

Participant will report their moderate-to-vigorous exercise minutes per week (over the past month) using a modified version of the Godin leisure time exercise questionnaire (Courneya et al., 2004; Godin & Shephard, 1985).

### **Analysis Plan**

With respect to the primary feasibility and acceptability outcomes, frequency values will be calculated for adherence to the program, number of weekly physical activity logs completed, number of Zoom group meetings attended, and number of post-intervention surveys completed. Descriptive statistics (mean, variance), skewness, and kurtosis will be calculated for the affective attitude items and the one item assessing program satisfaction. Cronbach’s alpha will be calculated for the four affective attitude items. A 2 x 2 within and between subjects ANOVA will be conducted to examine intervention by time effects on affective attitudes towards exercise. Effect sizes ( $\eta^2$ ) will also be calculated for the between, within, and interaction effects.

The interviews with participants will be transcribed verbatim. The transcripts will be analyzed using thematic analysis. First, codes will be generated to identify content that is relevant to understanding participants’ experiences with the program and virtual running crew/group. Second, codes will be analyzed to produce higher order themes regarding participants’ experiences with the program and virtual running crew/group (Clarke & Braun, 2017).

With respect to exploratory analyses, descriptive statistics (mean, variance), skewness, kurtosis, and Cronbach's alpha will be calculated for each secondary outcome variable. Multiple 2 x 2 within and between subjects ANOVAs will be conducted to examine intervention by time effects on perceived social support, flourishing, exercise-related subjective vitality, exercise identity, and exercise behaviour. Effect sizes ( $\eta^2$ ) will also be calculated for the between, within, and interaction effects.

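### The planned 2 x 2 ANOVA interaction is a change-score test with the baseline slope fixed at 1; estimating that slope is usually more precise and costs only SAP wording

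*Combined protocol and SAP*

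**What the plan says.** The Analysis Plan has one model for comparing the arms on measured outcomes. For affective attitudes, listed among the primary feasibility and acceptability outcomes: "A 2 x 2 within and between subjects ANOVA will be conducted to examine intervention by time effects on affective attitudes towards exercise". For the secondary outcomes: "Multiple 2 x 2 within and between subjects ANOVAs will be conducted to examine intervention by time effects on perceived social support, flourishing", and likewise exercise-related vitality, exercise identity and exercise behaviour. Alongside these it lists means, variances, skewness, kurtosis, Cronbach's alpha and eta-squared.

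Each of the six outcomes is measured twice. The first measurement precedes allocation (Data Collection: "Participants will be asked to complete baseline measures on Qualtrics before they are randomized to the intervention or control group") and the second is at Week 8. The Randomization section stratifies by gender: "We will stratify to ensure equal distribution of men and women across conditions". No section puts a baseline score or gender into a model as a covariate.

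The Aims section calls formal efficacy testing ill-advised in a pilot and gives the exploratory analyses another purpose: to "calculate statistical information such as effect sizes and measurement variance for informing power analyses when planning future efficacy trials".

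**The concern.** With two arms and two time points, the interaction contrast is the difference between arms in mean change. Testing it is the same as regressing the Week 8 score on arm with the baseline coefficient held at 1. That coefficient can be estimated from the data instead. When it is below 1, as is usual for self-report scales that are imperfectly correlated over eight weeks with similar spread at both times, the change score subtracts too much baseline noise and the interval is wider than it need be.

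The stake is efficiency, not bias. The pilot's product for later work is an estimate of effect and variability. A trial sized on the change-score variance would usually be larger than a baseline-adjusted trial requires. The quantity needed to plan the adjusted trial, the baseline to Week 8 correlation, is not among the listed outputs.

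**Working it through.** **Inputs from the document.** Two arms of 30 (N = 60); one pre-randomisation and one Week 8 measurement; stratification by gender. N = 60 is five cohorts of 12. There is no power calculation to reproduce.

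**Assumptions.** The document gives no SD, correlation, target effect, alpha or dropout rate. I take Week 8 SD = 1, r from 0.3 to 0.9, 60 completers, independent participants and two-sided 5%.

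**Step 1: equivalence.** On one simulated data set with 30 per arm, the interaction F was 4.9279, the squared t on change scores was 4.9279, and the F from the regression with baseline slope fixed at 1 was 4.9279.

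**Step 2: variances with equal SDs, n per arm.**

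- Change score: 2(1 − r) × 2/n
- Baseline-adjusted: (1 − r²) × 2/n
- Ratio: (1 − r²)/[2(1 − r)] = (1 + r)/2

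Estimating the slope has a small cost. With baseline and a balanced gender term at N = 60, the adjusted variance is multiplied by 1 + 1/55 = 1.018. Half-widths use t on 58 df (2.002) for the change score and 56 df (2.003) for the adjusted model. At r = 0.5:

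- Change: 2.002 × √(1.00 × 2/30) = 0.517
- Adjusted: 2.003 × √(0.75 × 2/30 × 1.018) = 0.452

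| r | Ratio, large sample | Ratio, 30 per arm | 95% half-width, change (SD) | 95% half-width, adjusted (SD) |
|---|---|---|---|---|
| 0.3 | 0.65 | 0.66 | 0.612 | 0.498 |
| 0.5 | 0.75 | 0.76 | 0.517 | 0.452 |
| 0.7 | 0.85 | 0.87 | 0.400 | 0.373 |
| 0.8 | 0.90 | 0.92 | 0.327 | 0.313 |
| 0.9 | 0.95 | 0.97 | 0.231 | 0.227 |

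Simulation with 20,000 trials per value of r gave ratios of 0.674, 0.763, 0.857, 0.920 and 0.969.

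**Step 3: unequal SDs.** Let k = SD(Week 8)/SD(baseline). Then Var(change) − Var(adjusted) is proportional to (1 − rk)². This is never negative, and it is zero when rk = 1, that is, when the true slope is 1. It matters for exercise minutes, because entry requires "not meeting the Canadian guidelines of 150 minutes of moderate-to-vigorous exercise per week", which narrows the baseline spread.

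- k = 1.5, r = 0.5: adjusted 2.25 × 0.75 = 1.6875; change 1 + 2.25 − 1.5 = 1.75; ratio 0.964.
- k = 2, r = 0.5: 3/3 = 1.00. At 30 per arm the slope cost makes it 1.018 (simulated 1.015).

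**Step 4: a later trial.** For an illustrative 0.5 SD effect with 80% power, the noncentral t uses d = 0.5/√[2(1 − r)] for the change score and d = 0.5/√(1 − r²) for the adjusted analysis, the latter on that model's residual degrees of freedom (2n − 3 or 2n − 4). No clustering allowance is included.

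| r | n per arm, change | n per arm, adjusted |
|---|---|---|
| 0.3 | 89 | 59 |
| 0.5 | 64 | 49 |
| 0.7 | 39 | 34 |
| 0.8 | 27 | 24 |
| 0.9 | 14 | 14 |

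The last two adjusted figures move by one with convention: 2n − 2 df gives 13 at r = 0.9, and charging the slope cost gives 25 at r = 0.8.

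**Step 5: gender.** Leaving out the stratification factor hardly changes true precision. If gender shifts the Week 8 score by an assumed 0.5 SD at r = 0.5, the simulated mean half-width of 0.531 implies a reported change-score SE of 0.531/2.0017 = 0.265, against a true 0.258: about 3% too large. With no gender effect there is no difference.

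**The case against.** The strongest reply is that this is a preference on exploratory outputs of a pilot. The planned estimate is unbiased, N was not set by power, the Aims speak of changes in these outcomes, and no decision threshold hangs on the tests. All of that is true, and it caps the importance of the point.

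The document also does not say that a later trial will be sized on change-score variance. That would be the later team's choice. The point is only that the planned outputs lean that way.

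Nor is r lost. Given the variances at each time and the interaction F, Var(change) can be recovered, and then r = (s0² + s1² − Var(change))/(2·s0·s1). On simulated data this returned 0.549 against an actual pooled value of 0.549. But the plan does not list F, and classical eta-squared without F is not enough. Reporting r directly is simpler.

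The gain is unknown for every outcome, is small at high r, and may be nil for exercise minutes. That stands, and it is why the wording is usually and not always.

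Finally, adjustment does nothing about clustering: "Participants in the virtual running group will be placed into running groups of six people". With groups of six in one arm and an assumed ICC of 0.01, 0.05 or 0.10, the variance of the arm difference is multiplied by [1 + (1 + 5 × ICC)]/2 = 1.025, 1.125 or 1.25, so the true SE is 1%, 6% or 12% larger than reported. This applies to the planned and the proposed analysis alike. It calls for a stated caveat and is no reason to keep the slope at 1.

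**Conclusion.** The concern holds. That the test is a change-score test is algebra. Under equal SDs, 60 completers and independent participants, baseline adjustment removes roughly 13% to 34% of the variance of the arm difference for r between 0.3 and 0.7, and about 3% at r = 0.9. The worst case, a true slope of 1, costs about 2%. The size for any particular outcome cannot be known from the document, because r is not given. Nothing here biases the estimates or touches the feasibility and acceptability aims. It is a worthwhile improvement to the figures meant for planning a later trial, not an error that invalidates the pilot.

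**What to change.** In the Analysis Plan, for affective attitudes and each of the five secondary outcomes now assigned to the ANOVAs:

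- Fit a linear model of the Week 8 score on arm, the baseline score of the same measure and gender, with participants analysed in the arm to which they were randomised.
- Report the adjusted mean difference with its 95% CI, the residual SD and the baseline to Week 8 correlation.
- Keep the 2 x 2 table of means and eta-squared as description.
- State that the intervals treat participants as independent and make no allowance for the running groups of six in the intervention arm.

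The cost is SAP wording only. Baseline scores and gender are already collected before randomisation, so no extra data, visits or participants are needed.
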